1.3 Background and Rationale

Hemophagocytic lymphohistiocytosis (HLH) or hemophagocytic syndrome (HPS) is an inflammatory disorder associated with the activation and expansion of reactive (i.e. non-clonal) macrophages. Primary HPS is associated with mutations (e.g. \approx 50% of familial cases are caused by perforin gene mutations) that culminate in defective natural killer (NK) cell and cytotoxic T-lymphocyte (CTL) degranulation and impaired killing of target cells. In these patients, a triggering event (e.g. viral infection) is associated with immune dysregulation that is characterized by the overproduction of proinflammatory cytokines (e.g. IL-12 and IFN- γ) and tissue accumulation of activated T-cells and macrophages.²⁷⁻³¹ These immunologic changes are associated with protean clinicopathologic manifestations, including: fever, hepatosplenomegaly, hyperferritinemia (due to macrophage activation), cytopenias (caused by phagocytosis - “hemophagocytosis”- of hematopoietic cells), hypofibrinogenemia, and multi-organ failure.³² Predominantly observed in children, primary HPS is initially managed with supportive care and chemotherapy, but is only curable in approximately 60% of children with allogeneic stem cell transplantation.^{3,33} In contrast to primary HPS, secondary HPS is more common in adults and is associated with a variety of triggers, including infection (often viral), autoimmunity, or hematologic malignancies (commonly non-Hodgkin lymphomas).³² For many patients, a precipitating cause cannot be identified. Apart from disease-specific therapies for patients in which a precipitating cause can be identified (e.g. non-Hodgkin lymphoma directed therapies for those with an underlying lymphoma), no HPS-specific therapies are currently available for the majority of adults with HPS. Therefore, these patients are frequently treated with a regimen originally developed for use in children with primary HPS that includes combinations of steroids, immunosuppressive agents (i.e. cyclosporine A), and etoposide. Not surprisingly, secondary HPS in adults is associated with high morbidity and mortality. In one of the largest single center studies, the overall mortality was 67%, with a median time from diagnosis to death of 35 (range: 5-160) days.² Therefore, improved therapeutic strategies for adults with secondary HPS are greatly needed.

Both pre-clinical and clinical data highlight the central role of proinflammatory cytokines, particularly IFN- γ , that are dependent upon the JAK/STAT signaling in HPS pathogenesis.²⁷⁻³¹ The disease biology and clinical manifestations associated with HPS are driven by this underlying “cytokine storm”, culminating in T-cell accumulation and macrophage activation. Therefore, inhibition of JAK/STAT signaling may represent a novel therapeutic approach. As ruxolitinib inhibits upstream Janus kinases (JAK) at nanomolar concentrations, and is well tolerated in myelofibrosis patients (and alleviates signs/symptoms associated with hypercytokinemia), we sought to determine whether it inhibits STAT1 phosphorylation in IFN- γ treated macrophages. Not surprisingly, ruxolitinib (1 μ M) was able to inhibit STAT1 phosphorylation in treated macrophages. Therefore, ruxolitinib represents a novel therapeutic

approach for secondary HPS that has the potential to dramatically change the standard of care (and improve outcomes) for these patients. Cytopenias (including thrombocytopenia) observed in HPS are secondary to consumption (“hemophagocytosis”) and cytokine-mediated suppression, and are not secondary to underlying bone marrow “failure”. Therefore, treatment will be initiated at 15 mg po twice daily.

2. OBJECTIVES

2.1 Primary Objective

To assess the efficacy of ruxolitinib 15 mg PO twice daily in patients with HPS.

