4.2 Exclusion Criteria

The presence of any of the following will exclude a patient from study enrollment.

1. CNS involvement
2. Malabsorption
3. Known secondary HPS that is otherwise treatable (e.g. non-Hodgkin's lymphoma).
4. Pregnant or lactating female: all females of child-bearing potential must have a negative serum pregnancy test within 7 days of treatment; lactating females must discontinue breast feeding.

5. Has received any prior systemic therapy, excluding corticosteroids, within 7 days (or 5 half-lives) of treatment.
6. Estimated creatinine clearance <15 mL/min
7. No active malignancy at the time of enrollment, except nonmelanoma skin cancers or carcinoma in situ. Patients with a prior history of malignancy are eligible if their malignancy has been definitely treated or is in remission and does not require ongoing adjuvant or cancer-directed therapies.
8. Active hepatitis B or hepatitis C or known HIV infection.
9. Known (and biopsy-confirmed) liver cirrhosis; or, a reported history of liver cirrhosis with a model for end-stage liver disease (MELD) score >20.

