6.1.1 Ruxolitinib Administration

Patients will receive Ruxolitinib at 15 mg twice daily orally either on an empty stomach or with food for 4 weeks (28 days) in a 4 week (28 day) cycle. Ruxolitinib will be administered in continuous 28-day cycles. For patients unable to ingest tablets, ruxolitinib suspended in water may be administered through a nasogastric (NG) or percutaneous endoscopy gastrostomy (PEG) tube. Tablets should be suspended (1 tablet in ~40 mL water) in water and stirred for 10 minutes and administered within 6 hours of dispersion with an appropriate syringe. The NG or PEG tube should be rinsed with ~75 mL water following administration.

Ruxolitinib administration must be at least 1 hour before or after any other medications.

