6.2 General Concomitant Medications and Supportive Care Guidelines

Because there is a potential for interaction of Ruxolitinib with other concomitantly administered drugs through the cytochrome P450 system, the case report form must capture the concurrent use of all other drugs, over-the-counter medications, or alternative therapies. The Principal Investigator should be alerted if the patient is taking any agent known to affect CYP3A4. In patients who concurrently take strong CYP3A4 inhibitors and a platelet count of at least 50,000 the dose of ruxolitinib should be capped at 10 mg twice daily due to the concern for increased serum concentrations of ruxolitinib's active metabolites. Strong CYP3A4 inhibitors, including grapefruit juice, should be avoided whenever possible.

Patients should receive full supportive care, including transfusions of blood and blood products, cytokines, antibiotics, anti-emetics, etc when appropriate.

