7. DOSING DELAYS / DOSE MODIFICATIONS

Ruxolitinib will be dosed twice daily throughout the study. In the event a dose is missed, the subject should be instructed to take the next scheduled dose.

Dose Level	Ruxolitinib (BID schedule)	
	CrCl \geq 60	CrCl 15-59
Level 1 (starting dose)	15 mg	10 mg
Level -1 (reduction)	10 mg	5 mg
Level -2 (reduction)	5 mg	Hold

Event Name	Nausea
Grade of Event	Management/Next Dose for Ruxolitinib
\leq Grade 1	No change in dose
Grade 2	Hold until \leq Grade 1. Resume at same dose level.
Grade 3	Hold* until $<$ Grade 2. Resume at one dose level lower, if indicated.**
Grade 4	Off protocol therapy
*Patients requiring a delay of $>$ 4 weeks should go off protocol therapy.	
**Patients requiring $>$ two dose reductions should go off protocol therapy.	
Recommended management: antiemetics.	

Event Name	Vomiting
Grade of Event	Management/Next Dose for Ruxolitinib
\leq Grade 1	No change in dose
Grade 2	Hold until \leq Grade 1. Resume at same dose level.
Grade 3	Hold* until $<$ Grade 2. Resume at one dose level lower, if indicated.**
Grade 4	Off protocol therapy
*Patients requiring a delay of $>$ 4 weeks should go off protocol therapy.	
**Patients requiring $>$ two dose reductions should go off protocol therapy.	
Recommended management: antiemetics; in the event a dose of ruxolitinib is vomited, it is recommended that subjects resume ruxolitinib with the next scheduled dose.	

Event Name	Diarrhea
Grade of Event	Management/Next Dose for Ruxolitinib
≤ Grade 1	No change in dose
Grade 2	Hold until ≤ Grade 1. Resume at same dose level.
Grade 3	Hold* until < Grade 2. Resume at one dose level lower, if indicated. **
Grade 4	Off protocol therapy
*Patients requiring a delay of >4 weeks should go off protocol therapy. **Patients requiring > two dose reductions should go off protocol therapy.	
Recommended management: Loperamide antidiarrheal therapy Dosage schedule: 4 mg at first onset, followed by 2 mg with each loose motion until diarrhea-free for 12 hours (maximum dosage: 16 mg/24 hours) Adjunct anti-diarrheal therapy is permitted and should be recorded when used.	

Event Name	Thrombocytopenia
Platelet Count	Management/Next Dose for Ruxolitinib
50,000-100,000	Level 1 Ruxolitinib
35,000-49,999	Level -1 (reduction) if determined to be secondary to Ruxolitinib per the discretion of the investigator or PI.
20,000-34,999	Level -2 (reduction)

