15.2 Analyses

Primary:

The primary analysis is the count of patients alive after 2 months since study entry. If 4 or more patients are alive at the 2 months assessment, the null hypothesis of a 15% survival probability at 2 months will be rejected in favor of our alternative hypothesis of a 60% survival probability. Ninety-five percent confidence intervals will be constructed based upon the exact binomial confidence interval. No loss-to-follow-up or censoring is expected prior to the study's primary endpoint assessment.

Secondary:

There are no formal response criteria for secondary HPS. Therefore, efficacy assessments (including appropriate laboratory studies) will be performed weekly (weeks 1-5), and every two weeks (weeks 6-12), and monthly (after 12 weeks), and responses determined as previously reported in a retrospective study.⁸ Briefly, a complete response is defined as

complete normalization of all quantifiable symptoms and laboratory abnormalities (described in the diagnostic criteria for HPS, above). A partial response is defined as at least a 25% improvement in two or more quantifiable symptoms/laboratory markers following the initiation of treatment. The best overall response is the best response recorded from the start of the treatment until disease progression/recurrence

Follow-up time will be calculated from the first administration of ruxolitinib, until death for OS or until disease-progression or death for PFS. Patients lost to follow-up will be censored on the date of their last known clinical assessment. Specifically for DOR, only patients having at least a PR to therapy are evaluable. Duration will be calculated from the date of the determination of partial response or better until the date of progression, death, or additional non-protocol therapy. Again, for patients lost to follow-up, duration will be censored at the time of last clinical assessment. The count and percentage of the number having an objective response (CR, CRu, or PR) will be reported along with confidence intervals. Product-limit estimates of Kaplan and Meier will be used to estimate OS, PFS, and DOR. The likelihood of loss to follow-up is expected to be extremely low.

Exploratory:

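### The objective and treatment sections give every patient 15 mg twice daily, but Section 7 starts eligible patients with creatinine clearance 15-59 mL/min on 10 mg, so such a patient has two starting doses on paper and the primary count tests an adjusted regimen

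*Combined protocol and SAP*

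**What the plan says.** Four places give a single dose. The synopsis and Section 2.1 state the primary objective as "To assess the efficacy of ruxolitinib 15 mg PO twice daily in patients with HPS". Section 1.3 ends with "Therefore, treatment will be initiated at 15 mg po twice daily". The regimen table in 6.1 lists 15 mg, and 6.1.1 says "Patients will receive Ruxolitinib at 15 mg twice daily orally either on an empty stomach or with food". None of them mentions renal function.

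The dose-level table in Section 7 has two columns. In the row beginning "Level 1 (starting dose", the entry is 15 mg for creatinine clearance of 60 or more and 10 mg for clearance 15-59. The renal exclusion in 4.2 (item 6) is "Estimated creatinine clearance <15 mL/min", so the second column describes eligible patients. Section 6.1 refers the reader to Section 7, but only for dose modifications.

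Section 6.2 adds that, with a strong CYP3A4 inhibitor and platelets of at least 50,000, "the dose of ruxolitinib should be capped at 10 mg twice daily".

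On the analysis, 15.2 states: "The primary analysis is the count of patients alive after 2 months since study entry". Four or more alive rejects the 15% null. Section 3.3 replaces only patients who never take a dose. No analysis set, tabulation or sensitivity analysis by dose is planned.

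**The concern.** There are two separate consequences.

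The first is operational. For a patient with clearance 15-59, someone working from 6.1.1 and someone working from Section 7 would write down different starting doses. The same conflict leaves unclear whether a 10 mg start for that patient follows the protocol or deviates from it.

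The second concerns what the trial may claim. The objective is specific to 15 mg twice daily, while the count that answers it includes everyone treated, including patients the protocol itself starts on, or caps at, 10 mg. A report using the objective's wording would attach the result to a dose that some of the counted patients were never assigned.

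**Working it through.** **The passages side by side, for an eligible patient with clearance 15-59 mL/min**

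| Place | Starting dose, twice daily |
|---|---|
| Synopsis and 2.1 (objective) | 15 mg |
| 1.3 | 15 mg |
| 6.1 table and 6.1.1 | 15 mg |
| Section 7, Level 1, clearance 15-59 | 10 mg |

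The conflict needs no assumption. Only its effect on the primary count does.

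**The plan's own figure.** Inputs from 15.1 and 15.2: n = 10, null 15%, alternative 60%, success at 4 or more alive.

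P(X ≥ 4 | 10, 0.15) = 1 − (0.1969 + 0.3474 + 0.2759 + 0.1298) = 0.050, which matches the 0.050 in the plan's table as a one-sided tail. At 60% the exact power is 0.945 against the stated 80%. That difference is a separate matter and does not affect this point.

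**How many patients might be on 10 mg.** The documents give no share with clearance 15-59 or on a strong inhibitor. Assume 10%, 20% or 30%, with the number k among 10 patients binomial:

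| Assumed share | P(k ≥ 1) = 1 − (1 − share)^10 | P(k ≥ 3) | P(k ≥ 4) |
|---|---|---|---|
| 10% | 0.651 | 0.070 | 0.013 |
| 20% | 0.893 | 0.322 | 0.121 |
| 30% | 0.972 | 0.617 | 0.350 |

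At least one such patient is likely across this range. Four or more is unlikely at the lower end and about one in three at the upper end.

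**What k does to the rule.** If k patients are on 10 mg, a positive result needs at least 4 − k survivors on 15 mg (none once k reaches 4). The chance of a positive result is P(A + B ≥ 4), with A ~ Binomial(k, survival at 10 mg) and B ~ Binomial(10 − k, survival at 15 mg). Two deliberately extreme assumptions bound the effect:

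| k | Fewest 15 mg survivors in a positive result | P(positive) if 15% at 15 mg, 60% at 10 mg | P(positive) if 60% at 15 mg, 15% at 10 mg |
|---|---|---|---|
| 0 | 4 | 0.050 | 0.945 |
| 1 | 3 | 0.098 | 0.912 |
| 2 | 2 | 0.177 | 0.862 |
| 3 | 1 | 0.291 | 0.790 |
| 4 | 0 | 0.430 | 0.692 |

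Pooling could therefore move the result either way. Nothing in the documents suggests that survival differs this sharply between the two groups.

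**An illustration and its limit.** Suppose 2 of 3 patients on 10 mg and 2 of 7 on 15 mg are alive. The rule is met. For the seven, P(X ≥ 2 | 7, 0.15) = 1 − 0.85^7 − 7 × 0.15 × 0.85^6 = 0.283, with an exact 95% interval of 4% to 71%. That interval contains both 15% and 60%, so seven patients settle little. The pattern can also arise with no dose difference. If survival is 60% at both doses and k = 3, a positive result with at most 2 of 7 alive on 15 mg has probability 0.0774 × 0.648 + 0.0172 × 0.216 = 0.054, or 0.054/0.945, about 6% of positive results.

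**The case against.** The best case for the plan is that the objective names the nominal regimen and everyone understands it to include the protocol's adjustments. Sections 1.2.3 and 6.2 present lower doses as responses to impaired renal function or higher drug concentrations, so fewer milligrams need not mean less exposure, and counting all treated patients is the natural analysis of such a regimen. This largely stands as a defence of the count. It does not rescue the wording, because the objective, 1.3 and 6.1.1 mention no adjustments. Nor do the documents show that exposure is equalised: 1.2.3 describes reductions of about 50%, whereas going from 15 mg to 10 mg is a reduction of one third.

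A reader might infer that a positive result need say nothing about 15 mg. The documents do not support that. It would take at least four of 10 patients on 10 mg, and no share is given. Section 15.1 also ties a positive result to further study of ruxolitinib, without naming a dose.

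A reader might also infer that the problem would stay hidden. That is too strong. Creatinine is measured at screening and on treatment (12.1.1, 12.2), the case report form captures all concurrent drugs (6.2), and dispensing records are kept (10.1.1). Each patient's dose can be recovered; what is missing is a planned tabulation.

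Finally, the 6.2 cap is narrow. It applies only with a strong inhibitor and platelets of at least 50,000, the section asks that such inhibitors be avoided where possible, and it may come into play after treatment starts.

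**Conclusion.** The inconsistency is certain and rests on the text alone: an eligible patient with clearance 15-59 mL/min has a 15 mg starting dose in 1.3, 6.1 and 6.1.1 and a 10 mg starting dose in Section 7. The primary count in 15.2 consequently evaluates a 15 mg regimen with protocol adjustments, which is not what the objective says.

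The effect on the trial's conclusion is uncertain and probably modest. With one or two of 10 patients on 10 mg, eight or nine of those counted are 15 mg patients. Larger effects need a larger share and a marked survival difference between the groups, both of which are assumptions here. The 4-of-10 rule itself need not change. The point is worth correcting because it touches what a patient is given and what the trial may claim, and because the correction is cheap.

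**What to change.** - Reconcile 1.3, 6.1 and 6.1.1 with 6.2 and the Section 7 table, so that each patient has one starting dose on paper. Which passage should prevail is for the sponsor and investigator; no view is offered here.
- Reword the objective in the synopsis and 2.1 as the efficacy of ruxolitinib at the protocol-assigned dose, including protocol-specified adjustments.
- Keep the 4-of-10 rule on all treated patients.
- In 15.2, add a purely descriptive line giving number alive over number treated by assigned starting dose, and note later reductions under the CYP3A4 cap or the Section 7 platelet table. A split by starting dose alone would miss those. With cells this small the line should carry no test and change no decision.

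The cost is wording in a few sections and one table row. Sample size and operating characteristics are unchanged. The downside is a headline claim slightly less specific to one dose.

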2.1.1 Primary Endpoint

Overall survival at two months.

2.2 Secondary Objective(s)

To assess the safety and tolerability of ruxolitinib in patients with HPS.

To determine the response rate, duration of response, progression-free survival, and overall survival in ruxolitinib treated subjects.

2.3 Exploratory Objectives

To assess inflammatory cytokines and markers of T-cell/macrophage activation (i.e. cytokines, sIL-2R, sCD163) as predictive biomarkers.

3. STUDY DESIGN

3.1 Study design including dose escalation / cohorts

Pilot study to determine the efficacy of Ruxolitinib in secondary hemophagocytic syndrome.

3.2 Number of Subjects

Up to 10 patients meeting the inclusion and exclusion criteria will be enrolled into this pilot study.

3.3 Replacement of Subjects

Subjects who do not receive the first dose of study drug will be replaced.

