12. STUDY PARAMETERS AND CALENDAR

12.1 Study Parameters

12.1.1 Screening Evaluation

Screening studies and evaluations will be used to determine the eligibility of each subject for study inclusion. All evaluations must be completed no longer than 14 days prior to administration of protocol therapy.

- Informed Consent
- Medical History
- Complete physical examination
- Vital signs including: blood pressure, pulse, respiratory rate, weight and temperature
- Concomitant Medications Assessment including prescription and herbal supplements
- Laboratory Studies:
 - Complete Blood Count (CBC) with differential and platelets.
 - Serum Chemistries: albumin, alkaline phosphatase, total bilirubin, bicarbonate, BUN, calcium, chloride, creatinine, glucose, potassium, total protein, SGOT [AST], SGPT [ALT], sodium.
 - β -HCG for women of childbearing potential at time of study entry
 - Ferritin
 - Lipids (Triglycerides)
 - Fibrinogen
 - Soluble IL-2 receptor
 - NK cell activity

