15. STATISTICAL CONSIDERATIONS

15.1 Sample Size

We will accrue and treat 10 patients on this pilot trial. We expect a 2-month survival rate approximating 15% in patients meeting the inclusion criteria with current standard of care. As we believe ruxolitinib may be highly active in this disease and change the current treatment paradigm, we believe the majority of treated patients will be alive at 2 months. Therefore, if 4 or more patients are alive 2 months following diagnosis, this would provide sufficient evidence to pursue ruxolitinib in an expanded cohort of patients in a future study. This design has 80% power to detect a survival rate of 60% versus an estimated survival rate of 15% using a 2-sided test, with 5% type I error. The operating characteristics for design are given in the table below for a range of true values for the probability of survival at 2 months, with at least 4 responders the critical value.

Probability of survival at 2 months following diagnosis	Probability therapy is deemed effective
0.05	0.010
0.15	0.050
0.25	0.228
0.35	0.488
0.45	0.738
0.55	0.901
0.65	0.978

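### Replacing enrolled patients who die before the first dose, with the 2-month clock starting before dosing, tilts the 4-of-10 rule towards a positive decision

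*Combined protocol and SAP*

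**What the plan says.** All references are to the combined protocol and SAP.

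- **Replacement (3.3):** "Subjects who do not receive the first dose of study drug will be replaced". The reason for not dosing plays no part.
- **Patients counted (15.1):** "We will accrue and treat 10 patients on this pilot trial".
- **Benchmark (15.1):** "We expect a 2-month survival rate approximating 15% in patients meeting the inclusion criteria with current standard of care". It is not stated to be conditional on living to a first dose, and no source is cited for it.
- **Clock:** 15.2 states "The primary analysis is the count of patients alive after 2 months since study entry", without defining study entry. The decision rule in 15.1 counts from diagnosis. Secondary overall survival in 15.2 counts from the first administration of ruxolitinib.
- **Decision (15.2):** the 15% null is rejected when at least 4 of the counted patients are alive at 2 months.
- **Gap before dosing (12.1.1):** "All evaluations must be completed no longer than 14 days prior to administration of protocol therapy". The calendar in 12.2 puts the same 14-day limit on its enrollment column and has a separate pre-treatment visit in the last 48 hours.
- **Early mortality (1.3):** in the cited single-center series, "the overall mortality was 67%, with a median time from diagnosis to death of 35 (range: 5-160) days".
- **Undosed patients:** Section 5 asks for a reason only when a consented patient is not enrolled. No section counts an enrolled patient's death before dosing as a failure, plans an all-enrolled analysis, or adjusts the 15%.

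**The concern.** Three provisions that are unremarkable singly work together here. The endpoint is early survival, the comparator is an external fixed rate, and the clock starts before the event that admits a patient to the count. A patient must survive from entry to first dose to be counted at all, and one who does not is replaced by someone who did. The 10 counted patients are then compared with a rate not described as applying to such survivors.

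What is at stake is the decision to pursue an expanded cohort. With 10 patients, exchanging one early death for a survivor can turn 3 alive into 4. As shown below, the rule already uses the whole 5% error, so there is no slack to absorb even a small shift.

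**Working it through.** **Inputs from the documents:** n = 10 treated; success if 4 or more are alive; null rate 0.15 (15.1, 15.2); gap from enrollment to treatment at most 14 days (12.1.1, 12.2); 67% mortality with a median of 35 days from diagnosis to death (1.3).

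**Inputs assumed:** the lag d from entry to first dose, and the shape of the survival curve. The documents give neither.

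**Step 1: the plan's own figure.** P(X ≥ 4 | n = 10, p = 0.15) = 0.04997, which matches the 0.050 tabulated in 15.1. This is a one-sided error.

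**Step 2: the null rate among dosed patients.** Let q be the share of enrolled patients who die before the first dose. If 15% of all enrolled patients are alive 2 months after entry, and only those who reach a dose are counted, the null rate becomes 0.15/(1 − q). With q set directly:

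| q | Null rate among dosed | P(X ≥ 4) |
|---|---|---|
| 0.05 | 0.158 | 0.059 |
| 0.10 | 0.167 | 0.070 |
| 0.20 | 0.187 | 0.100 |

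**Step 3: q as a function of the lag, clock at entry.** Two assumptions are used.

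- *A, cited series:* 67% die, with exponential times and a 35-day median among the deaths, so q = 0.67 × (1 − 0.5^(d/35)). This borrows only the early-death share from the series and keeps the plan's 15% at 2 months. It also places times measured from diagnosis on the interval from enrollment, which is an approximation.
- *B, constant hazard through 15% at 60.9 days:* h = −ln(0.15)/60.9 = 0.0312 per day, and q = 1 − exp(−h·d).

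| Lag d | A: q | A: null rate | A: P(X ≥ 4) | B: q | B: null rate | B: P(X ≥ 4) |
|---|---|---|---|---|---|---|
| 3 days | 0.039 | 0.156 | 0.057 | 0.089 | 0.165 | 0.067 |
| 7 days | 0.087 | 0.164 | 0.067 | 0.196 | 0.187 | 0.098 |
| 14 days | 0.162 | 0.179 | 0.087 | 0.353 | 0.232 | 0.184 |

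A 2-day lag under B gives 0.061.

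**Step 4: sensitivity to the shape of the hazard.** For Weibull curves through 15% at day 60, still with the clock at entry, front-loaded deaths (shape 0.7) give 0.087, 0.177 and 0.344 for lags of 2, 7 and 14 days. A rising hazard (shape 1.5) gives 0.052, 0.064 and 0.097.

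**Step 5: clock moved to first dose.** Under a constant hazard, survival over the 2 months after dosing is S(d + 60.9)/S(d) = 0.15 for every d, so the error returns to 0.050. With shape 0.7 (60-day version) it is 0.115 for a 7-day lag and 0.160 for 14 days.

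**The case against.** The strongest reply is that replacing undosed subjects is usual in a small treated-patient study, and that this pilot decides only whether to go on to a further cohort. Counting people who never took the drug blurs the question of drug activity. This stands, and it is why the 10-patient count should remain primary.

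It is also fair that the 15% has no cited source. The words about current standard of care could mean patients who received that care, in which case the benchmark may itself leave out some early deaths. The documents do not settle this, so the mismatch is a risk and not a demonstrated fact.

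A reader might infer more than the documents support, in four ways:

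- *That patients wait about two weeks.* The 14 days is the oldest that screening results may be. The documents do not give the actual interval, and the visit in the last 48 hours says nothing about its length.
- *That the exclusion on prior therapy builds in a week's wait.* Section 4.2 excludes a patient who "Has received any prior systemic therapy, excluding corticosteroids, within 7 days (or 5 half-lives) of treatment". This is an eligibility look-back that touches only recently treated patients. Someone still inside the window is not eligible, so a death then would ordinarily be a screen failure and not a replacement under 3.3.
- *That the error is 18%.* This needs the full 14-day lag and a constant hazard whose median survival is ln 2/0.0312, about 22 days. Using the mortality in 1.3, the same lag gives 0.087.
- *That correcting the time origin would not help.* Step 5 shows that, under a constant hazard, starting the clock at first dose removes the bias entirely. A residue needs front-loaded deaths, which the documents neither state nor exclude. The 35-day median in 1.3 describes only those who died and is counted from diagnosis.

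**Conclusion.** The point holds in a limited form. As written, 3.3, 15.1 and 15.2 let deaths between entry and first dose leave the primary count and credit the survivors with that interval. Nothing elsewhere in the plan offsets this, and the direction of the bias is towards a positive decision.

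The size cannot be fixed from the documents. It rests on an assumed lag, on 15% survival at 2 months in all enrolled patients, and on the clock starting at entry. The lower values quoted for 7 and 14 days use the series in 1.3, and the higher ones a constant hazard. Front-loaded deaths would give more and a rising hazard less. If diagnosis is the origin, as in 15.1, the guaranteed interval is at least as long. This is a cheap improvement worth making, not a flaw that invalidates the design.

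**What to change.** Keep 3.3 and the 10-patient primary count. Add to 15.2:

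- a supportive 2-month count from enrollment in all eligible enrolled patients, with those who died undosed counted as not alive, reported beside the primary count;
- the interval from enrollment to first dose for each patient;
- a statement, if 4 or more of the 10 are alive, of whether that result depends on deaths that were replaced.

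The three time origins in 15.1 and 15.2 should be reconciled in the same edit, because the size of the bias depends on which one governs the primary count.

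The cost is a few sentences and 2-month vital status for the undosed patients. These would be few: if 10% to 20% die before dosing, 10/(1 − q) gives about 11 to 12.5 enrolled for 10 treated. The supportive survival figure would be slightly less favorable and would include patients who never received the drug, so it should be labeled as such. If nobody dies before dosing, it shows that replacement played no part in the result.
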